cancer screening. Included in the intervention are women between the ages of 52 and 74, as of December 31, 2023. Excluded are women who have had a mammogram (screening, diagnostic, film, digital, or digital breast tomosynthesis) claim between October 1, 2021 and the monthly data pull preceding each monthly wave of outreach, as well as women who have not been continuously enrolled with GHP during that timeframe—i.e., they have had a gap in enrollment of greater than 45 days (or 1 month, for Medicaid beneficiaries) in a given calendar year, or any gap in enrollment between October 1 and the data pull for outreach. Also excluded are GHP members in hospice, using hospice services, or receiving palliative care in 2023. Excluded are Medicare members 66 years of age or above as of the date of the data pull for outreach who are either: (1) enrolled in an Institutional SNP any time during 2023, (2) living long-term in an institution during 2023, or (3) 66 years of age or above as of December 31, 2023 with both frailty and advanced illness (as defined by 1+ claim/encounter for frailty in 2023 and any of the following during 2022 or 2023: 2+ visits with a diagnosis of advanced illness, 1+ acute inpatient encounter with a diagnosis of advanced illness, 1+ acute inpatient discharge with advanced illness diagnosis, or a dispensed dementia medication). Finally, excluded are patients who had a bilateral mastectomy at any time before the data pull for outreach: bilateral mastectomy, unilateral mastectomy with a bilateral modifier, history of bilateral mastectomy, or any combination of codes indicating mastectomy on both left and right side. Mammogram screening evidence comes from GHP claims data, as well as Geisinger electronic health record data and St. Luke's University Health Network, WellSpan Health, PrimeMed Medical Group, Family Practice Center, and Equipt Health data, with GHP claims data trumping other sources except where claims are not on file. The intervention began on May 10, 2023.

At each wave, a random subset (as described above) of currently eligible patients will be randomized to all four of the following study arms:

1. Current **standard postcard** encouraging patients to schedule their mammograms and to contact Geisinger for help doing so.
2. **Formal letter** telling patients that they are overdue and including contact information as above
3. **Auto-dialer** voice message allowing patients to respond to schedule

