The outcome is determined according to HEDIS criteria and based on a combination of GHP claims data and other sources. The time frames vary according to the availability of appropriate comparator samples. Time frames are specified for each of the analyses below.

Question 1: Does calling people increase mammogram completions relative to other modalities of outreach?

We will test the hypothesis that live calls increase the probability of mammogram completions within 180 days of outreach, relative to other modalities.

Analysis 1 (Confirmatory): Time Frame: In the 180 days following the outreach

We will run an OLS regression including a categorical predictor variable coding for experimental arm (0 = live call, 1 = standard postcard, 2 = formal letter, 3 = auto-dialer). This analysis will include all enrolled patients.

Question 2: Do different modalities of outreach increase mammogram completions relative to no outreach?

We will test the hypothesis that each of the individual modalities increases the probability of mammogram completions within 120 days of outreach, relative to passive control groups.

Analysis 2.1 (Confirmatory): Time Frame: In the 120 days following the outreach

We will run an OLS regression including a categorical predictor variable coding for experimental arm (0 = passive control, 1 = standard postcard, 2 = formal letter, 3 = auto-dialer, 4 = live call). This analysis will include patients in the first 3 waves of active outreach, along with a passive control group consisting of the contemporaneous 120 days of the last 3 waves of outreach, during which outreach will not yet have occurred for those patients.

Other Pre-specified Outcomes

We will run the analyses described above on the following additional outcomes:

1. Mammogram completed – namely, do different modalities of outreach increase mammogram completions relative to each other? We will test whether individual modalities are differentially effective in increasing the probability of mammogram completions within 180 days of outreach, relative to each other (for those modalities not already compared by the analyses above).
[Time Frame: In the 180 days following the outreach]

We will run an OLS regression including a categorical predictor variable coding for experimental arm (0 = standard postcard, 1 = formal letter, 2 = auto-dialer), as well as a separate OLS regression (0 = formal letter, 1 = auto-dialer). This analysis will include patients in all 7 waves of outreach.

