2. Breast malignancy risk detected

High risk of malignancy, among patients visiting Geisinger clinics and, as available, outside Geisinger (yes/no)

[Time Frame: In the 210 days following the outreach]

3. Mammogram appointment scheduled

Appointment scheduled for mammogram, among patients visiting Geisinger clinics (yes/no)

[Time Frame: In the 30 days following the outreach]

Covariates

An interim call to action—calling or speaking with GHP for help with scheduling—may not be as helpful for patients typically seeking care at non-Geisinger clinics as those going to Geisinger health system clinics. Also, we may not get data on mammogram completions as reliably from outside the Geisinger system. Therefore, all the regressions described above will also explore including as a covariate and interaction term whether or not the patient has an attributed Geisinger PCP.

Analysis Notes

Recent work suggests that OLS regressions are appropriate in randomized experiments with binary outcome variables such as ours (Gomila, 2021).

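### The scheduling outcome is limited to Geisinger clinic visitors without saying when or from what data visiting is determined; if visits after outreach count, the arm comparison is no longer randomised

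*Combined protocol and SAP*

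**What the plan says.** SAP, Other Pre-specified Outcomes, item 3 reads "Appointment scheduled for mammogram, among patients visiting Geisinger clinics (yes/no", with "Time Frame: In the 30 days following the outreach". Item 2 reads "High risk of malignancy, among patients visiting Geisinger clinics and, as available, outside Geisinger (yes/no", with "Time Frame: In the 210 days following the outreach". Neither item says when visiting is determined or from what records. Nor does either say whether the phrase limits the denominator or describes where the outcome can be seen.

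The section opens with "We will run the analyses described above on the following additional outcomes". Those earlier analyses do not share one analysis set. For Analysis 1 the plan states "This analysis will include all enrolled patients". Analysis 2.1 uses the first three waves plus passive controls drawn from the last three.

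The Covariates section names a separate affiliation variable, "whether or not the patient has an attributed Geisinger PCP", as an exploratory covariate and interaction term. It gives no measurement date and does not link the variable to items 2 and 3.

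In the Protocol, Methods, the postcard encourages patients to schedule and "to contact Geisinger for help doing so". The letter carries the same contact information, the auto-dialer lets patients respond to schedule, and the live caller helps them schedule during the call.

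**The concern.** Randomisation makes the arms comparable in the full set of patients assigned, or in any subset fixed before assignment. It does not do so in a subset that the intervention can alter. Item 3 is worded as a restriction on who is counted, and the only time attached to it is the period after outreach. A programmer could reasonably select women with a Geisinger visit in that period.

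An arm that prompted more women to come to Geisinger would then have a larger and different denominator. The difference between arms would mix the effect on scheduling with the effect on who is counted. Exposure is greatest in Analysis 2.1, where the comparison group has had no outreach that could prompt a visit. In Analysis 1 every arm has outreach, so what matters is how far the arms differ in prompting visits.

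**Working it through.** The plan gives no scheduling rate, malignancy rate or share of patients visiting Geisinger, and its Power Analysis covers mammogram completion only. There is no planned figure to reproduce. The check is of the wording, followed by a hypothetical calculation.

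**Three readings of item 3**

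- *Visited Geisinger after outreach.* The group can be changed by the intervention, so the comparison is not randomised. This fits the wording and the time frame.
- *Usual source of care before outreach.* This is a valid randomised subgroup, only smaller. It fits the Covariates section, which contrasts patients by where they typically seek care, but the plan does not link that language to item 3.
- *A note on where data exist, with everyone analysed.* The full randomised set is kept. This fits the all-enrolled statement of Analysis 1, but the plan does not say that non-visitors are scored as no rather than dropped.

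The three readings give different denominators, and nothing in the SAP chooses between them.

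**What the first reading could do (all inputs assumed)**

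Let V be the share of patients who visit regardless of outreach and s the scheduling rate among them. Let d be the extra share who visit only because of outreach and q the fraction of those who schedule. Take the comparator as having d = 0, as for no-outreach controls, and no scheduling among non-visitors.

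- Difference over all randomised patients: d × q.
- Difference among visitors: (V × s + d × q)/(V + d) − s = d × (q − s)/(V + d).

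Assume V from 40% to 80% and d from 1 to 5 percentage points. Set s = 13.1%, borrowed from the plan's assumed 180-day completion rate because no scheduling rate is given.

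- q = 0, all-patient difference 0. With V = 0.8 and d = 0.01: 0.01 × (−0.131)/0.81 = −0.0016, or −0.2 points. With V = 0.4 and d = 0.05: 0.05 × (−0.131)/0.45 = −0.0146, or −1.5 points.
- q = 1, all-patient difference 1.0 to 5.0 points. With V = 0.8 and d = 0.01: 0.01 × 0.869/0.81 = 0.0107, or 1.1 points. With V = 0.4 and d = 0.05: 0.05 × 0.869/0.45 = 0.0966, or 9.7 points.

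The q = 0 case is the cleaner demonstration: the arms do not differ over all patients, yet a difference appears among visitors. In the q = 1 case part of the enlargement is simply the smaller denominator. The sign depends on whether q lies above or below s, which the documents do not tell us. If the group is fixed before randomisation, d = 0 in every arm and the distortion is zero.

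**Item 2**

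Its wording extends beyond Geisinger where data are available, so the calculation above does not carry over. What remains is that a high-risk finding may be recorded more or less completely depending on where a woman receives care after outreach.

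**The case against.** A reader might infer that the plan does condition on visits after outreach. The documents do not establish this. Visiting carries no date, the Covariates section speaks of habitual place of care in similar terms, and Analysis 1 is said to include everyone enrolled. That objection stands, and it limits the point to an undefined analysis set. It does not remove the point, because the benign readings are not written into item 3 either.

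A reader might also infer that both outcomes are confined to Geisinger visitors. For malignancy risk this is contradicted by the added words about data from outside Geisinger.

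The mechanism can be overstated. The Covariates section describes the call to action as calling or speaking with GHP, the health plan. Speaking with the plan is not a clinic visit, a booking need not lead to a visit within 30 days, and nothing says bookings are made only at Geisinger. This makes a large distortion less certain but does not exclude one, since outreach is meant to get women scheduled.

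Finally, a reader might try to express the bias as a multiple of the true effect. Suppose 30-day scheduling is 6% v 4% of all patients, 20–40% would visit anyway, and 50–100% of schedulers become visitors. The 2.0-point difference then appears as 3.25 to 6.95 points among visitors, about 1.6 to 3.5 times as large. That figure should not be used. Every input is invented, and the risk ratio among visitors is 1.40 to 1.48 against 1.50 overall, so most of the enlargement is the change of denominator. With equal scheduling rates that model gives no difference at all. Moreover, if all scheduling occurred among existing Geisinger users, an unbiased baseline subgroup would show 2.0/0.4 = 5 to 2.0/0.2 = 10 points.

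**Conclusion.** The concern holds in a limited form. The denominator of the scheduling outcome is not defined in time or source, and one natural way of following the words would compare selected rather than randomised groups, above all against the no-outreach controls. For malignancy risk the concern is smaller and is mainly one of ascertainment.

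The size cannot be derived from the documents. The hypothetical figures show only that distortion can go in either direction; they do not estimate it. The conclusion assumes that outreach could change who visits Geisinger, which the described arms make plausible but the documents do not quantify. Both confirmatory completion analyses stand as written. The change is still worth making, because it removes the possible bias under the first reading and settles the wording under the other two.

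**What to change.** Reword items 2 and 3 so that each is analysed over all patients in the corresponding randomised comparison: all enrolled patients for Analysis 1, and the specified waves with their controls for Analysis 2.1. Count no recorded event as no, and state that this is the main analysis.

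If a Geisinger-only analysis is wanted, make it supplementary. Define it by attributed Geisinger PCP as recorded at the data pull before randomisation or, for controls, at the data pull of the wave they are matched to. The Covariates section should give the same date for that variable.

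The cost is a few sentences in the SAP; the PCP variable is already planned. The Project Status section says no outcome data had been accessed at posting, so at that point the change could be made without knowledge of results.

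The downside is that absolute rates will be lower because outside appointments are not seen. Item 3 should therefore be labelled as an appointment recorded at Geisinger. The change keeps the compared groups as randomised but does not cure incomplete capture of outside events, and the report should say so for both outcomes.

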4. **Live call** from a GHP care gaps coordinator helping patients schedule while speaking with them.

The remaining patients will serve as contemporaneous controls for patients in the other arms, during the span of time prior to which they are included in an active outreach arm. The controls will include patients eligible for outreach at the time the comparison patients are randomized to the corresponding active arms; they will exclude patients who become eligible at a later date. For example, controls for patients in wave 2 will consist primarily of patients assigned to wave 6, excluding those wave 6 patients who will not have been eligible for outreach at the time of the wave 2 rollout. Additionally, to account for patients who are eligible initially but become ineligible over time, those patients will be randomized to control groups as available. In the example above, a random subset of patients who become ineligible prior to the rollout of other waves will be added to the wave 2 control group.

Finally, for analysis, given that control patients do not have an intervention send date, the starting date will be randomly chosen for each to match one of the treatment arms' send dates.

Power Analysis

With 17,640 patients, we would have 80% power to detect a 2.5% absolute increase in mammograms with two-tailed alpha of .05, between each among standard postcard, letter, and auto-dialer arms, and live calls, assuming a 13.1% baseline incidence of mammograms completed within 180 days. The detectable increase becomes 1.8% when comparing across no-outreach controls and each among standard postcard, letter, and auto-dialer arms, or 3.0% across controls and live calls, assuming an 8.9% mammogram incidence within 120 days. The outcome duration varies according to the availability of appropriate comparator samples. The target effect size and number of patients are informed by practical considerations regarding the anticipated number of eligible women in 2023, the acceptable duration of the intervention (approximately 7 months), the acceptable delay between intervention and outcome being recorded, and effects that seem achievable and useful if achieved.

Project Status

Outreach has begun, as of May 10, 2023 (IVR and live calls) and May 12, 2023 (postcards and letters). No outcome data have been accessed as of the time this file was posted.

Statistical Analysis Plan

Planned Analyses

Primary Outcome: Mammogram completed

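### The confirmatory regressions contain only the arm term; fixing Geisinger PCP attribution and a few other baseline variables in them is a small, free precision gain, not the repair of an error

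*Combined protocol and SAP*

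**What the plan says.** Under Planned Analyses, Analyses 1 and 2.1 are labelled confirmatory and share one specification: "We will run an OLS regression including a categorical predictor variable coding for experimental arm". No other term is listed for either.

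The Covariates section then says that all the regressions "will also explore including as a covariate and interaction term" whether the patient has an attributed Geisinger PCP. It gives two reasons. Scheduling help from the health plan may be less useful to patients who get their care elsewhere, and mammograms done outside the Geisinger system may be recorded less reliably.

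Age and Medicare or Medicaid status appear only in Methods, as eligibility variables. Wave structures the randomisation (Design) and the choice of controls (Methods), but it is in no model.

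The Power Analysis section starts "With 17,640 patients" and claims "80% power to detect a 2.5% absolute increase in mammograms with two-tailed alpha of .05" for live call against each other modality, "assuming a 13.1% baseline incidence of mammograms completed within 180 days". The comparisons with no outreach are made "assuming an 8.9% mammogram incidence within 120 days". For the mail and auto-dialer arms the section says "The detectable increase becomes 1.8% when comparing across no-outreach controls and each among standard postcard, letter, and auto-dialer arms". Its figure for the live-call arm at the same 120-day rate is "or 3.0% across controls and live calls".

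**The concern.** The plan names a baseline variable, gives a reason to expect it to predict the recorded outcome, and leaves it out of the confirmatory models. In OLS on a binary outcome, main effects for baseline predictors lower the residual variance and leave the arm coefficient on the risk-difference scale. The stated power is set at 80% with no reserve, so even a small gain is worth having if it costs nothing.

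Analysis 2.1 adds a second reason. Its controls are not a simple parallel arm. They are later-wave patients who were already eligible at the earlier rollout, supplemented by a random subset of those who became ineligible before their own wave. A group assembled in this way can differ from the active patients in measured characteristics.

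**Working it through.** **Arm sizes (derived; the documents do not state them).** Equal waves are assumed, with the live-call cap of 300 per wave from Design.
- Wave size: 17,640 / 7 = 2,520.
- Live call: 300 per wave; 7 × 300 = 2,100 in all, and 3 × 300 = 900 in three waves.
- Each other arm: (2,520 − 300) / 3 = 740 per wave; 7 × 740 = 5,180 in all, and 3 × 740 = 2,220 in three waves.
- Controls for Analysis 2.1 (last three waves): 3 × 2,520 = 7,560.

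**The plan's own figures.** Power = Φ[(d − 1.96·SE0) / SE1]. SE0 uses the pooled proportion and SE1 the two separate proportions; the test is two-sided at 0.05.
- Live call v each other modality, 15.6% v 13.1%, n = 2,100 v 5,180: (0.025 − 1.96 × 0.00893) / 0.00920 = 0.815, power 79.3%. The detectable difference at 80% is 2.53 points. The stated 2.5 reproduces.
- Control v live call, 8.9% v 11.9%, n = 7,560 v 900: (0.030 − 1.96 × 0.01020) / 0.01128 = 0.887, power 81.3% (75.8% to 79.8% with unpooled, continuity-corrected or arcsine versions). The detectable difference is 2.95 points. The stated 3.0 reproduces.
- Control v each mail or auto-dialer arm, 8.9% v 10.7%, n = 7,560 v 2,220: (0.018 − 1.96 × 0.00701) / 0.00733 = 0.580, power 71.9%. The detectable difference is 2.00 points. The stated 1.8 does not reproduce.

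**Effect of adjustment.** If the covariates explain a share R² of outcome variance, both standard errors shrink by √(1 − R²), which is equivalent to n / (1 − R²) patients. R² is an assumption throughout.

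| Contrast | none | 0.5% | 1% | 2% | 3% | 5% | 10% |
|---|---|---|---|---|---|---|---|
| Live v other, +2.5 | 79.3 | 79.4 | 79.6 | 80.0 | 80.4 | 81.2 | 83.2 |
| Control v mail/auto-dialer, +1.8 | 71.9 | 72.1 | 72.3 | 72.7 | 73.2 | 74.0 | 76.2 |
| Control v live, +3.0 | 81.3 | 81.4 | 81.6 | 82.0 | 82.3 | 83.1 | 84.9 |

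Between 0.5% and 3% the gain is about 0.2 to 1.3 points of power, and the standard error falls by 0.25% to 1.5%. The 1.8-point contrast would need R² of about 18% to reach 80%.

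**Which R² is plausible.** For a binary covariate with share s, R² = s(1 − s)(high − low)² / [p(1 − p)]. Assume half the patients have a Geisinger PCP and a two-fold rate ratio around 13.1%, that is 17.5% v 8.7%. Then R² = 0.25 × 0.088² / (0.131 × 0.869), about 1.7%. For 30% to 70% attributed and rate ratios of 1.25 to 2, R² is about 0.1% to 1.9%. Reaching 5% from PCP alone at an even split would take roughly 20.6% v 5.6%.

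**Imbalance in Analysis 2.1 (illustration, assumed values).** A 5-point difference in PCP share combined with a 10-point difference in recorded completion shifts the unadjusted contrast by 0.05 × 0.10 = 0.5 points, against a target of 1.8. Chance alone would not produce this. At a 50% share the standard error of the difference in share is √[0.25 × (1/7,560 + 1/2,220)] = 1.2 points, so 5 points is about four standard errors. It would have to come from the way the controls are assembled.

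**The case against.** The strongest reply is that nothing here is wrong. Arm-only OLS estimates the risk difference validly under randomisation, the gain is small, and its size is assumed. All of that stands.

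Part of the prognostic argument also weakens. That scheduling help may matter less to non-Geisinger patients describes effect modification, which the exploratory interaction already addresses. Only the reason about outcome recording supports a main effect. Its size is unknown, because every patient is a health plan member and claims are the leading source. The documents do not say that age or coverage type predicts completion in this overdue group.

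Three stronger readings are tempting, and the documents do not support them.
- *The trial is underpowered throughout and covariates would cure it.* Two of the three stated differences reproduce. The third falls short because 1.8 points does not fit three active waves, and no plausible R² repairs that.
- *The sponsor can choose the adjusted or unadjusted result after seeing the data.* The arm-only models carry the confirmatory label and the PCP models are described as additional, so the primary model is already fixed.
- *Adjustment makes the Analysis 2.1 controls comparable.* It removes imbalance only in the variables that are entered. Selection through later eligibility is not captured by PCP, age or coverage.

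**Conclusion.** The point holds as a low-cost improvement. Both confirmatory models leave out a baseline variable that the plan itself expects to relate to how reliably the outcome is recorded, along with two variables already held for eligibility. The expected benefit is about 0.2 to 1.3 points of power, on an assumed R² of 0.5% to 3% and arm sizes derived from equal waves and the 300-call cap. The protection against measured imbalance in Analysis 2.1 is a further benefit, whose size the documents do not allow one to estimate. Adjustment does not recover mammograms that go unrecorded outside Geisinger.

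Wave belongs in the model for a reason of its own. When a wave has more than 1,200 patients the live-call share is 300 divided by the wave size, so allocation varies if wave sizes do, and controls are matched by calendar period. With exactly equal waves the share is constant and wave adds only precision.

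**What to change.** Prespecify one confirmatory model for each analysis:
- arm;
- attributed Geisinger PCP, as recorded at the data pull;
- age, linear;
- coverage type (Medicare, Medicaid, other);
- randomisation wave in Analysis 1, and the matched calendar wave in Analysis 2.1.

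All covariates enter as main effects. Keep the PCP-by-arm interaction exploratory, with PCP centred so that the arm coefficient remains an average effect and does not become the effect in one PCP group. Report the arm-only model as a sensitivity analysis. Do not add earlier mammogram history on condition that the records allow it: the eligibility look-back begins on October 1, 2021, and a conditional term would leave the model open.

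The 1.8-point figure in Power Analysis should be corrected or explained separately, since this change does not resolve it.

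The cost is SAP wording. The variables are used for eligibility or allocation, or are already named in the SAP, and Project Status says that no outcome data had been accessed at posting.
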